	
allowing the study to be stopped early for efficacy. A second interim analysis is planned at approximately, but no less than, 250 deaths, with a two-sided p-value ≤ 0.0151 allowing the study to be stopped early for efficacy.
 
A conditional power of less than or equal to 15% at each of the interim analyses will result in the study stopping early for futility.
 
Sample size modification will be considered at the second interim analysis following the approach described in Mehta & Pocock (2011)¹⁶ which employs an un-weighted test statistic at the final analysis as recommended by Burman & Sonneson (2006)¹⁷.
 
Final Analysis of primary endpoint: The final analysis, without a sample size modification, will be performed when approximately, but no less than, 417 deaths have occurred. A two-sided p-value ≤ 0.0363 is required to declare a statistically significant improvement in median OS at the final analysis.
 
If the sample size is increased after the second interim analysis, the final analysis will be performed when approximately, but no less than, 564 deaths have occurred, which will result in 80% power to detect an improvement in median OS from 10.7 to 13.7 months using a log rank test with a final two-sided alpha of 0.0363.
 
Analysis of secondary efficacy endpoints
 
Comparison between treatment groups for all secondary endpoints will be conducted at the final analysis with a two-sided alpha of 0.05.
 
Time to event endpoints (ie, TTP, TTUP, TTSP) will be compared between treatment arms using a log-rank test. Tumor response rates will be compared between treatment arms using the continuity adjusted Newcombe-Wilson test. The FACT-Hep score will be compared between treatment arms using a mixed linear model with baseline score and the relative time from baseline as covariates.
 
Safety Analysis: All patients who received study treatments at least once will be included in the safety analysis. All Adverse events (AEs) will be reported according to the National Cancer Institute Common Terminology Criteria for Adverse Events v 4.0 (CTCAE) grades and coded using the Medical Dictionary for Regulatory Activities (MedDRA). The incidence of treatment emergent adverse events (events which were not present at baseline or worsened in severity following the start of treatment) will be summarized according to MedDRA primary system-organ class (SOC) and preferred term (PT). Laboratory values will be summarized by treatment group over time and overall.
 
A feasibility safety assessment will be conducted after the first 20 patients in the treatment group have received both TS and sorafenib therapy.
 
Poolability and Other Analysis: Multivariate Cox regression analysis of time-to-event efficacy endpoints will be conducted on stratification criteria and other factors such as age, gender, duration of disease prior to randomization.
 
As a sensitivity analysis, to address the poolability of data across regions, study sites and gender, a Cox regression analysis of the primary efficacy endpoint, OS, will be conducted with factors of region, study site and gender, and to determine the impact of these factors on OS. Note: region and study site will not be included simultaneously in the model due to collinearity.
 
Should the impact of region, site or gender on OS be statistically and clinically relevant, the reasons for the observed differential treatment effect, such as patient

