10.0 STATISTICS

10.1 SAMPLE SIZE ESTIMATE

This study is a randomized open label multi-center Phase III adaptive trial using a group sequential design with a primary endpoint of overall survival (OS).

The study is designed to detect a 3.5 month increase in median OS from 10.7 months in the control arm to 14.2 months in the TheraSphere arm (i.e., hazard ratio = 0.754), using a log rank test.

A maximum of 417 deaths will yield 80% power to detect the target difference in median OS (ie, HR=0.754) with a two-sided alpha of 0.05 using a group sequential design with 2 interim analyses and stopping boundary defined by the rho family error spending function with rho=1.5 (Jennison and Turnbull, 2000)¹⁸. It is estimated that a maximum of 520 patients will need to be recruited over 60 months, with an 18 month additional follow-up period. This includes an adjustment to take account of an assumed 5% of patients who will be lost to follow-up and for whom a date of death is not recorded, and an assumed additional 5% of patients who will be erroneously randomized because they did not meet the eligibility criteria at randomization.

Sample size modification will be considered at the second interim analysis using the approach described in Mehta and Pocock (2011)¹⁶ which employs an un-weighted test statistic at the final analysis as recommended by Burman and Sonneson (2006)¹⁷. If the sample size is increased after the second interim analysis, the final analysis is planned when approximately, but no less than, 564 deaths have occurred, which will result in 80% power to detect an improvement in median OS from 10.7 to 13.7 months (ie, hazard ratio=0.781) using a log rank test with a final two-sided alpha of 0.0363. It is estimated that approximately 700 patients will need to be recruited over 66 months, with an 18 month additional follow-up period, in order to observe 564 deaths. This includes an adjustment to take account of an assumed 5% of patients who will be lost to follow-up and for whom a date of death is not recorded, and an assumed additional 5% of patients who will be erroneously randomized because they did not meet the eligibility criteria at randomization.

Sample size calculations were performed and verified with PROC SEQDESIGN, SAS 9.3.

[REDACTED]

[REDACTED]

[REDACTED]

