10.2.3.1 PRIMARY ENDPOINT STATISTICAL ANALYSIS PLAN

Overall survival (OS) time will be calculated as the interval between the randomization date and the date of death for any cause, with censoring at the date of last contact for patients alive. The Kaplan-Meier method will be used to estimate the OS curves in the two treatment groups; comparison between the curves will be performed using the log-rank test.

Interim Analyses: Two interim analyses of OS are planned to be performed by the Independent Data Monitoring Committee (IDMC) based on group sequential stopping rules using an alpha boundary defined by the rho family error spending function with rho=1.5. The first interim analysis is planned at approximately, but no less than, 188 deaths, with a two-sided p-value ≤ 0.0151 allowing the study to be stopped early for efficacy. A second interim analysis is planned at approximately, but no less than, 250 deaths, with a two-sided p-value ≤ 0.0151 allowing the study to be stopped early for efficacy.

A conditional power of less than or equal to 15% at each of the interim analyses will result in the study stopping early for futility, using the method described in Proschan et al (2006)¹⁹.

Sample size modification will be considered at the second interim analysis using the approach described in Mehta and Pocock (2011)¹⁶.

[figure not shown]
Final Analysis: The final analysis, without a sample size modification, is planned when approximately, but no less than, 417 deaths have occurred. A two-sided p-value ≤ 0.0363 is required to declare a statistically significant improvement in median OS at the final analysis.

If the sample size is increased after the second interim analysis, the final analysis is planned when approximately, but no less than, 564 deaths have occurred, which will result in 80% power to detect an improvement in median OS from 10.7 to 13.7 months using a log rank test with a final two-sided alpha of 0.0363.

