7.4 Interim Analyses and Data Monitoring

An IDMC will be established to oversee the conduct of the study. The IDMC will meet periodically during the study to review enrollment, protocol deviations and safety events for the study. In addition, the IDMC will conduct and review the interim efficacy results and will make formal recommendations to the study Sponsor at the time of the interim analysis and during the conduct of the study.

After the first 20 patients in the treatment group have received TheraSphere followed by at least 2 weeks of sorafenib therapy, a feasibility safety assessment will be conducted. The IDMC will review the safety results of both the control and treatment groups in an unblinded fashion. The IDMC will take into consideration the established safety profiles of TheraSphere and sorafenib as described in the package inserts for each product as well as the published literature. The expected high rates of AEs events and death that are associated with disease progression in patients with HCC will be considered.

A consideration for stopping further enrollment to the trial may be made if there is a pattern of serious toxicity clearly related to the sequential administration of TS followed by sorafenib. Such a toxicity pattern must be clearly different from, or more severe than, what might be expected from independent administration of the products. The potential adverse impact of any such pattern of toxicity on the survival or well being of the patient should be considered in the context of the safety and outcome expectations of patients with advanced HCC.

This study uses an adaptive group sequential design with two interim analyses and one final analysis. The efficacy stopping boundaries are based on the rho family error spending function with the parameter value rho=1.5. The first interim analysis is planned at approximately, but no less than, 188 deaths, with a two-sided p-value ≤ 0.0151 allowing the study to be stopped early for efficacy. A second interim analysis is planned at approximately, but no less than, 250 deaths, with a two-sided p-value ≤ 0.0151 allowing the study to be stopped early for efficacy. If the interim analyses do not occur at exactly 188 or 250 deaths, the corresponding efficacy boundaries were to be calculated using the rho family spending function with rho=1.5.

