The boundary for the final analysis will be adjusted based on the first and second interim analyses and the actual number of deaths at the final analysis. The actual number of deaths for the first and second interim analyses were 205 and 257, respectively. However, at the first interim analysis, the efficacy boundary was inadvertently not recalculated based on the actual number of 205 deaths, and instead the p-value scale boundary stated in the SAP, based on the planned number of 188 deaths, was used. The p-value scale boundary at the second interim analysis was based on the planned number of 188 deaths at the first interim analysis, the actual number of 257 deaths at the second interim analysis and the planned final number of 417 deaths. Therefore, for the final analysis, the efficacy boundary (i.e., α_f) will be calculated using the rho family spending function with $\rho=1.5$, based on the planned number of 188 deaths at the first interim analysis, the actual number of 257 deaths at the second interim analysis and actual number of deaths at the final analysis. This will result in a more conservative efficacy boundary than the one using actual numbers of deaths for all scenarios for the actual number of deaths at the final analysis, as shown in Table 8. The efficacy boundary α_f will be fixed and documented prior to database hard lock for the final analysis. A two-sided p-value $\leq \alpha_f$ will be required to declare a statistically significant improvement in OS at the final analysis.

Table 8 Scenarios of Efficacy Boundary at Final Analysis

Actual Number of Deaths at Final Analysis	Two-Sided P-value Scale Efficacy Boundary at Final Analysis	
Based on 188 Planned Deaths at IA1, 257 Actual Deaths at IA2 and Actual Number of Deaths at Final Analysis	Based on 205 Actual Deaths at IA1, 257 Actual Deaths at IA2 and Actual Number of Deaths at Final Analysis	

Actual Number of Deaths at Final Analysis	Two-Sided P-value Scale Efficacy Boundary at Final Analysis	
	Based on 188 Planned Deaths at IA1, 257 Actual Deaths at IA2 and Actual Number of Deaths at Final Analysis	Based on 205 Actual Deaths at IA1, 257 Actual Deaths at IA2 and Actual Number of Deaths at Final Analysis
406	0.0354	0.0355
407	0.0354	0.0355
408	0.0355	0.0356
409	0.0355	0.0356
410	0.0356	0.0357
411	0.0356	0.0357
412	0.0356	0.0358
413	0.0357	0.0358
414	0.0357	0.0358
415	0.0358	0.0359
416	0.0358	0.0359
417	0.0358	0.0360

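### SAP Table 8 rescales interim alpha already spent to the actual final death count, so for fewer than 417 deaths the final OS threshold falls when it should rise

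*Protocol*

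**What the plan says.** The protocol (synopsis and 10.2.3.1) plans two interim looks and a final analysis at 417 deaths: "The first interim analysis is planned at approximately, but no less than, 188 deaths, with a two-sided p-value ≤ 0.0151", then "A second interim analysis is planned at approximately, but no less than, 250 deaths, with a two-sided p-value ≤ 0.0151", and at the end "A two-sided p-value ≤ 0.0363 is required to declare a statistically significant improvement in median OS at the final analysis". SAP 7.4 gives the rule behind these boundaries: "The efficacy stopping boundaries are based on the rho family error spending function with the parameter value rho=1.5".

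SAP 7.4 then records what happened. "The actual number of deaths for the first and second interim analyses were 205 and 257, respectively". At the first interim the boundary was not recalculated for 205 deaths, and the planned 188-death boundary was applied. The second interim boundary was computed from 188 deaths at the first look, "the actual number of 257 deaths at the second interim analysis and the planned final number of 417 deaths". The sample size was not increased. Because 417 deaths had become unlikely (406 had occurred when version 4.0 was prepared), the final analysis takes place at 417 deaths or on 30 April 2022, whichever is first.

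The final threshold is to be computed from 188, 257 and the actual final count. Table 8 column 1 gives it as 0.0354 at 406 deaths, rising to 0.0358 at 417. Column 2, which uses 205 in place of 188, gives 0.0355 to 0.0360. Of the column 1 rule the SAP says "This will result in a more conservative efficacy boundary than the one using actual numbers of deaths". The threshold is to be fixed and documented before hard lock.

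**The concern.** The interim looks are past, and the boundaries applied there were set with 417 as the final count. The alpha they used cannot change because the trial ends with fewer deaths. If the remaining alpha is fixed and the final look moves closer to the second interim, the two statistics become more strongly correlated. A patient population that did not cross at the second look is then less likely to cross a given bar at the end under the null, so the p-value threshold must go up. Table 8 goes down.

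This number decides the primary endpoint, and the secondary hierarchy in SAP 8.6.2 opens only if it is met. A p-value between the Table 8 entry and the corrected value would be declared a failure although the 5% error rate would still hold. The SAP expects a final count below 417, so the affected rows are the likely ones.

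**Working it through.** **Inputs.** Two-sided alpha 0.05 and a 417-death plan (protocol 10.1); rho = 1.5; planned looks at 188 and 250; actual looks at 205 and 257; final count D from 406 to 417 (SAP 7.4).

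**Method.** Cumulative two-sided spending is 0.05 × t^1.5. The log-rank Z-scores have correlation √(d_j/d_k), with information equal to deaths. Boundaries c1, c2, c3 are solved in turn by numerical integration so that the probability of first crossing at each look equals the spending increment (one-sided 0.025, doubled).

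**1. The plan's own figures.** Looks at 188/250/417 give 0.0151, 0.0151 and 0.0363, matching the protocol. Power at HR 0.754 is 79.8% (stated 80%).

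**2. Table 8, column 1.** It reproduces, to last-digit rounding, when the spending times are 188/D and 257/D. That gives 0.03539 (406), 0.03556 (410), 0.03573 (414) and 0.03585 (417), against 0.0354, 0.0356, 0.0357 and 0.0358 in the table.

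**3. Interim alpha charged.**
- Set against 417: 0.05 × (188/417)^1.5 = 0.0151 after the first look and 0.05 × (257/417)^1.5 = 0.0242 after the second. The boundaries are p ≤ 0.0151 and p ≤ 0.0160. The second is re-derived; the SAP does not print it.
- Implied by Table 8 at 406: 0.05 × (188/406)^1.5 = 0.0158 and 0.05 × (257/406)^1.5 = 0.0252. The boundaries would be 0.0158 and 0.0167, which were not the ones used.

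**4. Interim spending held at the 417-based values.** The remaining alpha is 0.05 − 0.0242 = 0.0258. The correlation of the second interim with the final look is √(257/417) = 0.785 at 417 deaths and √(257/406) = 0.796 at 406.

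| Final deaths | Table 8 col. 1 | Spending held (first look counted at 188) | Full alpha at actual 205/257 timing |
|---|---|---|---|
| 406 | 0.0354 | 0.03623 | 0.03746 |
| 410 | 0.0356 | 0.03609 | 0.03731 |
| 414 | 0.0357 | 0.03595 | 0.03717 |
| 417 | 0.0358 | 0.03585 | 0.03707 |

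At 417 deaths the first two columns are the same calculation.

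**5. Overall two-sided error of the Table 8 rule.** If the first look is counted at 188: 0.0493 at 406 deaths and 0.0500 at 417. At the actual timing (205 deaths with p ≤ 0.0151, 257 with p ≤ 0.0160) the interims spent only 0.0231, and the overall error is 0.0482 at 406 and 0.0489 at 417.

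**6. Cost at 406 deaths, true HR 0.754, actual timing.** Critical HR = exp(−2z/√406).

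| Threshold | z | Critical HR | Power |
|---|---|---|---|
| 0.0354 | 2.1038 | 0.8115 | 78.5% |
| 0.0362 | 2.0947 | 0.8123 | 78.7% |
| 0.0375 | 2.0807 | 0.8134 | 79.1% |

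**7. Column 2 is not a valid yardstick.** It too rescales past spending. It implies a first-look boundary between 0.05 × (205/417)^1.5 = 0.0172 and 0.05 × (205/406)^1.5 = 0.0179, neither of which was applied.

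**The case against.** The strongest reply is that Table 8 computes correctly from its stated inputs, errs on the safe side, and comes after an openly admitted lapse at the first interim. A sponsor that then takes the stricter threshold is acting defensibly, and loosening it late in an open-label trial has a credibility cost. The amounts are small: the choice matters only for a p-value between 0.0354 and about 0.0362, or 0.0375 if all alpha is recovered.

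Most of this stands, and it limits the weight of the point. It does not explain why rows below 417 should assume interim boundaries that the same section says were not used.

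A reader might also infer more than the documents support:
- **That the protocol's 0.0363 is wrong, or in unresolved conflict with the SAP.** It is exact for its own plan. The SAP discloses the change, and Appendix 5 provides for recalculation when an interim misses its planned count.
- **That the whole step from 0.0363 to 0.0358 is an error.** At 417 deaths it follows from the second look falling at 257 rather than 250.
- **That the SAP calls the loss negligible.** It says only that its column is the stricter of the two, and prints both.
- **That the threshold ought to be 0.0371 to 0.0375.** Those values would use the full alpha, but they recover it from the sponsor's own omission at the first interim. That is a debatable choice, not a required correction.

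**Conclusion.** The point holds for SAP 7.4 and the Table 8 rows below 417 deaths. For those rows the rule charges interim alpha that was not spent, and the threshold moves the wrong way: 0.0354 instead of about 0.0362 at 406 deaths, with the gap closing to nothing at 417.

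The error is conservative. Type I error is not inflated; at the actual timing it is 0.0482 to 0.0489 against 0.05. The power cost at 406 deaths is about 0.2 point against the 0.0362 correction and 0.6 point against full alpha. The correction is worth making because this is the primary decision threshold and the remedy is one recalculation, not because the trial's power is at risk.

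The result assumes information proportional to deaths, a first look counted at 188 as in the SAP, and a second interim boundary of 0.0160 re-derived from the inputs that the SAP names. Using rounded interim boundaries (0.0151 and 0.0160) does not change the full-alpha thresholds.

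**What to change.** In SAP 7.4, state that cumulative interim spending stays fixed at the values set against 417 deaths (0.0151 and 0.0242, two-sided) and that the remaining alpha is spent at the actual final count. Replace the Table 8 rows below 417 accordingly: about 0.0362 at 406, 0.0361 at 410 and 0.0359 at 414 deaths (0.03595 before rounding), with 0.0358 at 417 unchanged. Print the boundary that was applied at the second interim.

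Reword the sentence on conservatism. It should say that both Table 8 columns rescale past spending, and that at the actual 205/257 timing the Table 8 rule gives an overall two-sided error of 0.0482 to 0.0489, where full alpha would allow 0.0375 at 406 deaths and 0.0371 at 417.

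The cost is one boundary recalculation and a few sentences, through the documentation step before hard lock that the SAP already requires. The inputs are death counts and boundaries already applied, not treatment effects. The downside is a slightly less strict threshold set late in an open-label trial, so the change must be dated and documented before any unblinded final result. If that moment has passed, the Table 8 value should stand and the corrected figure be reported alongside it. The protocol's 0.0363 needs no correction.

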2.0 TRIAL SCHEMA

3.0 SCHEDULE OF EVENTS

Evaluation/Test	Screen	Rand-omize	Sorafenib for the Control Group	1st TS work up & Adminis-tration	2nd TS work up & Adminis-tration	Sorafenib for the Treatment Group	TS work up & re-treatment ¹	Follow Up Until Death
Timing of Visit(s)	Days -14 to 0	Day 0	Weeks 1-4 initiate Weeks 5 & thereafter continue therapy	Weeks 1-4	Weeks 5-8	> 2 & < 6 weeks after TS – initiate & thereafter continue therapy	After hepatic progression	Q 8 weeks ± 14 days ⁸
Informed Consent	X							
Demographics	X							
Medical History	X							
Physical Exam (PE)	X							
ECOG Performance Status	X			X	X		X	X
Medication & Prior Treatment History	X							
Review Eligibility Criteria	X							
Hematology: WBC, Hgb, Hct, Platelet	X		X ⁷	X ⁷			X	X
Coagulation: PT, PTT, INR	X		X ⁷	X ⁷			X	X
Chemistry panel, liver function tests	X		X ⁷	X ⁷			X	X

Evaluation/Test	Screen	Rand-omize	Sorafenib for the Control Group Weeks 1-4 initiate Weeks 5 & thereafter continue therapy	1st TS work up & Adminis-tration	2nd TS work up & Adminis-tration	Sorafenib for the Treatment Group > 2 & < 6 weeks after TS – initiate & thereafter continue therapy	TS work up & re-treatment ¹ After hepatic progression	Follow Up Until Death	
	Days -14 to 0			Weeks 1-4	Weeks 5-8			Prior to PD ⁹	Post PD
Serum Pregnancy ²	X						X		
Tumor makers for HCC (AFP)	X		X	X				X	
Liver Volume/Mass Calculation				X			X		
Randomize Patient		X							
Hepatic Angiogram, Tc-MAA ¹⁰ scan, TS Dose Calculation ³ ,				X	X		X		
Order TS ³				X	X		X		
Administer TS ^{3, 4, 10}				X	X		X		
Administer Sorafenib ⁵			X			X	X ⁶		
QOL questionnaire	X							X	
Triple Phase MRI/ Spiral CT of abdomen	X							X	
Child-Pugh score	X							X	

Evaluation/Test	Screen	Rand-omize	Sorafenib for the Control Group Weeks 1-4 initiate Weeks 5 & thereafter continue therapy	1st TS work up & Adminis-tration	2nd TS work up & Adminis-tration	Sorafenib for the Treatment Group	TS work up & re-treatment ¹	Follow Up Until Death	
	Days -14 to 0			Weeks 1-4	Weeks 5-8	> 2 & < 6 weeks after TS – initiate & thereafter continue therapy		Q 8 weeks ± 14 days ⁸	
Spiral CT of chest and pelvis	X							X	
Assess/Report Adverse Events	X		X	X	X		X	X	
Review/Record Concurrent Medication	X		X	X	X		X	X	
Final Endpoint Efficacy/Safety documentation & exit patient								X	X

¹ Additional TS work up & Administration in lesions amenable to further TS treatment² Female patients of childbearing potential only

³ TS patients only

⁴ Additional TS treatments may be administered only after progression if lesions are amenable to treatment

⁵ According to package insert at Weeks 1-4 for Control group patients and after all initial TS administrations for Treatment group patients only

⁶ Sorafenib to be stopped 7 days before subsequent TS administration on disease progression and restarted 2 weeks after TS is administered

⁷ If treatment commences within 14 days of randomization the clinical laboratory assessments are not required to be repeated.

⁸ The follow-up visits should be scheduled from the day of randomization. A window of ± 14 days is permissible from the scheduled date.

⁹ Progression of disease resulting in termination of further treatment

¹⁰ If available, ⁹⁹mTc-MAA SPECT or SPECT-CT taken as part of the TS planning and post TS treatment imaging (Y-90 SPECT-CT or Y-90 PET-CT or Y-90 PET-MRI) taken as part of the TS administration quality control, will be collected retrospectively for exploratory analysis

